6.3 Long Term Treatment Period

All subjects will enter the long term treatment period after Week 2, although dose adjustment may continue in Switch subjects and titration may continue in Rollover subjects.

During long term treatment, all subjects will be contacted by telephone at Week 3 and will return to the clinic on Weeks 4, 8, 15, 28 and every 13 weeks thereafter for evaluation of safety and chorea control. In addition, Rollover subjects will have an additional telephone contact at Week 5. Switch subjects will have an additional telephone contact at Week 7, to remind subjects to complete diary card before the Week 8 visit. **Subjects who have not achieved a dose level that adequately controls chorea and is well tolerated by the Week 4 visit (Switch subjects) or Week 5 telecon (Rollover subjects) should have unscheduled visits or telephone contacts in order to further adjust their dose upward or downward.** Site interactions for dose adjustment should alternate between telephone contacts and clinic visits. During long-term treatment, further dose adjustments of SD-809 ER may be made, if necessary, but not more often than weekly and in increments of 6 mg (6 mg/day or 12 mg/day after a total daily dose of 48 mg is reached). Dose adjustments should be based on all available information including the subject's and caregiver's reports of adverse events and chorea control, information from rating scales and all safety evaluations. If subjects become non-ambulatory or require more aid than an assistive device during long term treatment, they will be permitted to remain in the study.

At the end of the long term treatment period, subjects will undergo a comprehensive evaluation, including physical and complete neurological exam, safety labs and 12-lead ECG and performance of all rating scales.

6.3.1 Telephone Contacts (One week prior to Baseline visit [Switch only]; Week 3 ± 3 days [All Subjects]; Week 5 ± 3 days [Rollover only]; Week 7±3 days [Switch only])

See the Schedule of Events A and B for a detailed summary of activities.

All subjects will be contacted by telephone during Week 3 to assess adverse events, chorea control (in consultation with the subject and caregiver), concomitant medication use, evaluation of study drug dose level and adjustment, if necessary and to schedule/confirm the next visit. Following the above assessments, study medication will be re-ordered according to specified procedures.

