8.3 Safety Analyses

Safety and tolerability will be assessed throughout the study by monitoring the following parameters:

 • Adverse events (AEs) • Clinical laboratory tests • Physical examination • Vital signs • 12- lead ECGs • Epworth Sleepiness Scale (ESS) 	
 • Columbia Suicide Severity Rating Scale (C-SSRS) • Unified Huntington’s Disease Rating Scale (UHDRS) • Swallowing Disturbance Questionnaire (SDQ) • Unified Parkinson’s Disease Rating Scale (UPDRS), dysarthria item • Barnes Akathisia Rating Scale (BARS) • Hospital Anxiety and Depression Scale (HADS) • Montreal Cognitive Assessment (MoCA©)
---	--

Safety data will be summarized descriptively for the overall population and based on prior treatment [SD-809 ER or placebo (Rollover subjects) or tetrabenazine (Switch subjects)]. Descriptive statistics will be calculated for quantitative data and frequency counts and percentages will be provided for categorical data. Descriptive statistics of change-from-baseline for Rollover subjects will utilize the Baseline from Study SD-809-C-15 (C-15 Baseline) and the Baseline from the present study (C-16 Baseline), as appropriate, and will be specified in the Statistical Analysis Plan.

The nature, frequency, and severity of adverse events will be tabulated for all subjects combined and by treatment. Baseline, within study, end of study, and change-from-baseline values for clinical laboratory evaluations and vital signs will be summarized as appropriate.

Treatment-emergent adverse events and laboratory, vital sign, and ECG parameters will be summarized. In addition, change from baseline will be summarized for laboratory and vital sign parameters. Shift tables will be provided for clinical laboratory results. ECG results will be classified as normal and abnormal and summarized.

8.4 *Safety Endpoints*

The following safety endpoints will be assessed:

- Incidence of adverse events (AEs), serious AEs, severe AEs, drug related AEs, AEs leading to withdrawal during the following periods:
 - Overall
 - During titration in Rollover subjects (up to 8 weeks)
 - During dose adjustment in Switch subjects (up to 4 weeks)
 - During long term treatment
- Observed values and changes from baseline in clinical laboratory parameters (hematology, chemistry, and urinalysis)
- Observed values and changes from baseline in vital signs
- Observed values in ECG parameters and abnormal findings

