- Number of subjects with on-treatment QTcF values > 450ms, > 480ms, > 500ms
- Observed values and changes in UHDRS, UPDRS (dysarthria), BARS, HADS, ESS, C-SSRS, and MoCA©
- Duration of time to achieve stable doing of SD-809 ER

8.5 *Sample Size*

Because this is an open label safety study, the sample size is not based on statistical considerations.

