7.2 Safety Endpoints

Safety and tolerability will be assessed throughout the study by monitoring the following:

- Incidence of adverse events (AEs), serious AEs (SAEs), severe AEs, drug-related AEs, and AEs leading to withdrawal during the following periods:
 - The entire post-baseline period
 - During the Titration Period (from Day 1 to the end of Week 8) in Rollover subjects
 - During the Dose-Adjustment Period (from Day 1 to the end of Week 4) in Switch subjects
 - During the Extended Dose-Adjustment Period (from Day 1 to the end of Week 8) in Switch subjects who undergo dose adjustment between Weeks 4 and 8 (if at least 10% of Switch subjects have had a dose adjustment between Week 4 and Week 8)
 - During the Stable-Dose Period (Week 8 to end of study)
- Observed values and changes from baseline in clinical laboratory parameters (hematology, chemistry, and urinalysis)
- Observed values and changes from baseline in vital signs
- Observed values in ECG parameters and abnormal findings

- Numbers of subjects with QTcF values > 450 msec, > 480 msec, > 500 msec
- Counts and percentages for Columbia Suicide Severity Rating Scale (C-SSRS)
- Observed values and changes from baseline in the following:
 - Unified Huntington Disease Rating Scale (UHDRS)
 - Unified Parkinson's Disease Rating Scale (UPDRS) (dysarthria)
 - Barnes Akathisia Rating Scale (BARS)
 - Hospital Anxiety and Depression Scale (HADS)
 - Epworth Sleepiness Scale (ESS)
 - Montreal Cognitive Assessment (MoCA[®])
 - Swallowing Disturbance Questionnaire (SDQ)
- Duration of time to achieve a stable dose of SD-809, defined as the number of days from Day 1 until the first day at which the subject was taking the dose level they were receiving at Week 8.

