9.9.5 Electrocardiogram (ECG)

A safety electrocardiogram (ECG) will be recorded at Screening and the Week 8 visit for all subjects. For subjects on allowed doses of citalopram or escitalopram, additional ECGs will be performed at Week 1 (Switch subjects) or Week 2 (Rollover subjects) and at Week 4 if the dose of study drug has been increased since the last ECG.

A cardiologist will provide a clinical interpretation of each ECG that will be recorded in the eCRF. ECG parameters that will be recorded include heart rate, PR interval, QRS duration, QT interval, and QTcF (QT interval corrected for heart rate using Fridericia's formula).

Descriptive statistics will be used to summarize ECG parameters at Screening and the Week 8 visit. Descriptive statistics will also be used to summarize QTcF values at Screening and the Week 8 visit for subjects with a QTcF value >450 msec at any visit. These analyses will be repeated for the Screening, Week 1 (Switch subjects) or Week 2 (Rollover subjects), Week 4, and Week 8 visits for subjects receiving allowed doses of citalopram or escitalopram at Baseline.

The number and percentage of subjects with normal, abnormal not clinically significant, abnormal clinically significant, and abnormal with clinical significance not specified ECGs will be summarized at Screening and the Week 8 visit. The number and percentage of subjects with PR >200 msec, QRS >100 msec, QT >500 msec, QTcF >450 msec, QTcF >480 msec, and QTcF >500 msec, will be similarly summarized. These analyses will be repeated for the Screening, Week 1 (Switch subjects) or Week 2 (Rollover subjects), Week 4, and Week 8 visits for subjects receiving allowed doses of citalopram or escitalopram at Baseline.

ECG results will also be listed.

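### SAP 9.9.5 counts QTcF exceedances at Screening and Week 8 only, so the End of Treatment/ET ECG is left out of an on-treatment safety endpoint

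*SAP*

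**What the plan says.** Protocol 8.4 lists two ECG endpoints: "Observed values in ECG parameters and abnormal findings" and "Number of subjects with on-treatment QTcF values > 450ms, > 480ms, > 500ms". SAP 7.2 keeps the thresholds but drops the on-treatment qualifier: "Numbers of subjects with QTcF values > 450 msec, > 480 msec, > 500 msec". Neither list names a visit.

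Protocol 6.3 states that at the end of long-term treatment "subjects will undergo a comprehensive evaluation, including physical and complete neurological exam, safety labs and 12-lead ECG". Protocol 6.3.3 repeats the ECG for End of Treatment/ET and has drug stopped at that visit. Both schedules of events show it, as do SAP Tables 1 and 2.

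SAP 9.9.5 describes collection differently: "A safety electrocardiogram (ECG) will be recorded at Screening and the Week 8 visit for all subjects". Its tables follow that description:

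- ECG parameters: "Descriptive statistics will be used to summarize ECG parameters at Screening and the Week 8 visit".
- Normal/abnormal classes: the same two visits.
- Threshold counts: "QTcF >450 msec, QTcF >480 msec, and QTcF >500 msec, will be similarly summarized".
- A further table gives "QTcF values at Screening and the Week 8 visit for subjects with a QTcF value >450 msec at any visit".

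Subjects on citalopram or escitalopram at Baseline get repeat tables that add Week 1 (Switch) or Week 2 (Rollover) and Week 4. All ECG results are listed. SAP 8.10 declares two changes from the protocol, the compliance range and the reclassification of the chorea and motor scores. Neither concerns ECGs.

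**The concern.** The endpoint is a number of subjects over a period, the time on treatment. The analysis section turns it into a count at one on-treatment visit for most subjects, and its account of what is recorded omits an ECG that the SAP's own schedules require. A subject whose QTcF is below 450 ms at Week 8 and above it at End of Treatment meets the protocol's endpoint but appears in no threshold count.

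The study's purpose is long-term safety, and the protocol treats QT as a matter of interest: it sets QTcF entry limits, restricts QT-prolonging drugs and adds ECGs for two antidepressants. At stake is whether the reported QTcF counts can be read as the on-treatment result or only as a Week 8 snapshot.

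**Working it through.** The documents give no figure to reproduce. The check compares the schedule with the tables and then traces where each late or unplanned ECG goes.

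**1. Scheduled on-treatment ECGs per subject**

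- Not on citalopram/escitalopram: Week 8 and End of Treatment/ET, so 2 scheduled. Tabulated: Week 8, so 1 of 2.
- On citalopram/escitalopram: Week 1 or 2, Week 4 if the dose has risen since the last ECG, Week 8, and End of Treatment/ET, so 3 or 4 scheduled. Tabulated: 2 of 3 or 3 of 4.
- Taking only the two ECGs common to everyone, with the planned cohort sizes and full attendance: Rollover 80 of 2 × 80 = 160; Switch 36 of 2 × 36 = 72.

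**2. Where End of Treatment, ET and unscheduled ECGs go under SAP 8.9**

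These are assigned by study day (SAP Table 3). An unscheduled record is used only when the scheduled record for that visit is missing. In the table, users means subjects on citalopram/escitalopram at Baseline.

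| Study day | Window | Tabulated in SAP 9.9.5? |
|---|---|---|
| 1–10 | Week 1 | Switch users only |
| 11–17 | Week 2 | Rollover users only |
| 18–24 | Week 3 | No |
| 25–31 | Week 4 | Users only |
| 32–52 | Weeks 5 and 7 | No |
| 53–80 | Week 8 | Yes, if the scheduled Week 8 ECG is missing |
| 81 onward | Week 15 to Week 171 | No |

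So every End of Treatment, ET or unscheduled ECG after Day 80 is outside the tables. For non-users, so is every such ECG before Day 53. A non-user who stops on Day 40 and has an ET ECG that day falls in the Week 7 window and has no on-treatment ECG in any summary table. Within Days 53–80, an unscheduled exceedance is passed over if a scheduled Week 8 ECG exists.

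**3. Whether the table of subjects above 450 ms at any visit closes the gap**

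A late exceedance can select a subject into it, but it does not supply the endpoint:

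- It displays only Screening and Week 8 values, so the exceeding value is not shown.
- Screening exceedances also select subjects. Women with QTcF up to 460 ms, and subjects with right bundle branch block up to 480 ms, are eligible (exclusion criterion 11).
- It does not separate 480 or 500 ms.

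**4. Size**

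The subjects missed are those above a threshold on an untabulated on-treatment ECG but not on a tabulated one. The documents give no exceedance rate, so only a conditional range is possible. Assume two ECGs per subject (Week 8 and End of Treatment) with the same exceedance probability p at each:

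- Same subjects exceed at both: share missed = 0.
- Independent ECGs: share missed = 1 − p / [1 − (1 − p)²] = (1 − p) / (2 − p). For p = 0.01 this is 0.99/1.99 = 0.497; for p = 0.10 it is 0.90/1.90 = 0.474.

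Repeated QTcF values in one subject are likely to be positively correlated, which puts the share between 0 and about one half under these assumptions. If exceedances became more frequent with time, it could be higher.

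Per subject, at full attendance, one person missing from the on-treatment count is 1/80 = 1.25 percentage points in Rollover or 1/36 = 2.8 points in Switch. SAP 8.7 uses non-missing denominators, so the actual shift would be somewhat larger.

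**The case against.** The strongest reply is that nothing is hidden. All ECG values are listed. A clinically significant abnormality that leads to intervention or diagnosis is an adverse event under protocol 7.1.1. A subject who first exceeds 450 ms at End of Treatment, and has a Screening or Week 8 ECG, adds to the number of observations in the table of subjects above 450 ms at any visit. That is true, and it rules out any claim that late exceedances are lost. But a listing is not a count, and that table mixes in Screening exceedances and does not grade severity.

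Second, endpoint lists seldom name visits, and protocol section 8 leaves analysis detail to the SAP. This also stands in part: silence about visits is not a promise to tabulate every visit. The argument rests instead on the protocol's on-treatment qualifier, which defines a period that includes the End of Treatment ECG.

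Third, the Week 8 limit may be deliberate. SAP 9.9.3 does the same for orthostatic vital signs, which are collected at End of Treatment/ET but summarised at Baseline and Week 8. A reader who saw that laboratory results are summarised at each visit might infer that ECGs were singled out; the orthostatic section shows they were not. The parallel does not justify the limit, and SAP 8.10 declares neither case.

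Finally, the study is descriptive with no formal testing, and the SAP allows further analyses. Those would, however, be labelled unplanned, whereas this endpoint is prespecified.

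**Conclusion.** The point holds. As written, SAP 9.9.5 gives a Week 8 count, with earlier visits for citalopram/escitalopram users, in place of the on-treatment count in protocol 8.4, and it does not declare the change. For most subjects half of the scheduled on-treatment ECGs are tabulated, and the omitted one is the only ECG scheduled after Week 8. It is a defect of reporting that should be corrected; no data are lost.

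The conclusion assumes that End of Treatment ECGs are taken while the subject is still on drug. This follows from stopping drug at that visit, but it may fail for some ET visits.

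Two stronger readings are not supported. One is that the reported counts understate QTcF risk by a known amount: the number of subjects missed is not given and is zero if the same subjects also exceed at Week 8. The other is that the limit conceals QTcF at the highest doses in Rollover subjects, who start at 6 mg/day and can still be titrated upward after Week 8. Neither document gives a relation between dose and QTcF or says how many subjects would go higher, and the dose is not to be raised once chorea is controlled.

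**What to change.** In SAP 9.9.5:

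1. Correct the description of ECG collection, and add End of Treatment/ET to the ECG parameter, QTcF and normal/abnormal summaries and to the table of subjects above 450 ms at any visit.
2. Base the 450, 480 and 500 ms counts, by cohort, on each subject's maximum on-treatment QTcF over all post-baseline ECGs, including End of Treatment, ET and unscheduled ones. Restore the on-treatment qualifier in SAP 7.2.
3. State an on-treatment rule for ET ECGs taken after the last dose. The protocol's 48-hour limit for the ET pharmacokinetic sample is one candidate, but it was set for another purpose and would need its own reason here.

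If a Week 8 analysis is what the sponsor wants, declare it in SAP 8.10 and word SAP 7.2 to match. The orthostatic summaries in SAP 9.9.3 could be checked at the same time.

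The cost is SAP text and programming. The ECGs and dosing dates are already collected, so no visit or procedure is added.

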 - Escitalopram (Lexapro or Cipralex)¹ is allowed when administered according to approved labeling.
 - Citalopram (Celexa)² is allowed when administered according to approved labeling.
 - See [Appendix 16](#) for Celexa and Lexapro (Cipralex) dosing information
 - See Appendix 12 for a complete list of prohibited or restricted QT prolonging drugs.
11. Subject has a QTcF value >450 ms (males) or >460 ms (females), or >480 ms (with right bundle branch block) on 12-lead ECG at Screening.
- Note: Subjects with left bundle branch block are not eligible.
12. Subject has evidence of hepatic impairment at Screening, as indicated by:
- AST or ALT >2.5 times the upper limit of normal.
 - Alkaline phosphatase (ALP) or total bilirubin (TBil) >2 times the upper limit of normal (ULN)
 - Note: Subjects with Gilbert's Syndrome are eligible to participate if approved by the Clinical Monitor.
 - Note: Subjects with abnormalities in two or more of these analytes (AST, ALT, ALP, TBil) must be approved by the Clinical Monitor in order to be enrolled.
 - Prothrombin time > 4 sec prolonged.
 - Positive Hepatitis B surface antigen (HBsAg).
13. Subject has evidence of significant renal impairment at Screening, indicated by a creatinine clearance <50 mL/min, as estimated by the Cockcroft-Gault formula.
14. Subject has known allergy to any of the components of study medication.
15. Subject has participated in an investigational drug or device trial other than SD-809-C-15 within 30 days (or 5 drug half-lives) of Screening, whichever is longer.

¹ Escitalopram (Lexapro or Cipralex): The maximum allowed dose is 20 mg/day. The maximum dose for subjects ≥ 65 years old is 10 mg/day.

² Citalopram (Celexa) is allowed with the following restrictions (See Appendix 16):

- d) If the subject is a known CYP2C19 poor metabolizer, Celexa is not allowed.
- e) If the subject is > 60 years old or is receiving cimetidine, omeprazole, esomeprazole, fluconazole, fluoxetine or ticlopidine, the maximum allowed dose is 20 mg/day.
- f) If the subject is ≤ 60 years old and is not receiving any of the medications in (b) above, the maximum allowed dose is 40 mg.

16. Subject is pregnant or breast-feeding at Screening or Baseline.
17. Subject acknowledges present use of illicit drugs at Screening or Baseline.

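### SAP 9.9.5 shows QTcF only as observed values and raw counts by visit: no within-subject change, shift or new-onset summary, and no End of Treatment/ET ECG

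*SAP*

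**What the plan says.** **Endpoints.** Protocol 8.4 lists "Number of subjects with on-treatment QTcF values > 450ms, > 480ms, > 500ms". SAP 7.2 lists "Numbers of subjects with QTcF values > 450 msec, > 480 msec, > 500 msec", without the on-treatment qualifier. For other ECG parameters, both documents name observed values and abnormal findings only.

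**Analysis.** SAP 9.9.5 states: "Descriptive statistics will be used to summarize ECG parameters at Screening and the Week 8 visit". The sentence on overall ECG interpretation ends "clinical significance not specified ECGs will be summarized at Screening and the Week 8 visit". The next sentence adds the interval cut-offs, including "QTcF >450 msec, QTcF >480 msec, and QTcF >500 msec, will be similarly summarized", so the QTcF counts refer to the same two visits. Subjects on allowed citalopram or escitalopram also get Week 1 (Switch) or Week 2 (Rollover), and Week 4. The SAP will also "summarize QTcF values at Screening and the Week 8 visit for subjects with a QTcF value >450 msec at any visit", and ECG results are listed.

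**Entry limit.** Protocol 4.3, item 11, excludes a subject if "Subject has a QTcF value >450 ms (males) or >460 ms (females), or >480 ms (with right bundle branch block) on 12-lead ECG at Screening".

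**ECG schedule.** Schedules A and B, in both documents, require a 12-lead ECG at Week 8 and at End of Treatment/ET. Protocol 6.3.3 repeats the latter. SAP 9.9.5 does not mention it.

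**Other safety data.** Change from baseline is planned for vital signs (SAP 9.9.2), chemistry and hematology, which also get shift tables (9.9.6), and the quantitative rating scales (9.9.7). No such summary is planned for ECG.

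**The concern.** The protocol treats QT as a risk: it has a QTcF entry limit, a list of prohibited or restricted QT-prolonging drugs, and extra ECGs for citalopram and escitalopram users. The useful question is whether QTcF rose within subjects on SD-809, by how much and in how many. Separate counts at two visits show only a net difference. They do not show how many subjects newly crossed 450 ms, and they miss any rise that ends below it. A long-term study whose ECG tables stop at Week 8 also leaves later on-treatment QTcF out of the planned summaries.

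**Working it through.** **1. Entry limits against SAP cut-offs.** Values that an eligible subject x can already have on the Screening ECG:

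| Group (entry limit) | Above 450 ms | Above 480 ms | Above 500 ms |
|---|---|---|---|
| Men without RBBB (450) | none | none | none |
| Women without RBBB (460) | 450 < x ≤ 460 | none | none |
| RBBB (480) | 450 < x ≤ 480 | none | none |

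Only the 450 ms row can hold pre-existing values. In an eligible subject, a Week 8 value above 480 or 500 ms is necessarily new relative to the Screening ECG.

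**2. What two visit counts identify.** Let S and W be the numbers above 450 ms at Screening and Week 8, P the number above at both, and n the number with both ECGs. New exceedances = W − P, where P lies between max(0, S + W − n) and min(S, W). For illustration, take S = W = 4 and n = 116. Then P lies between max(0, 4 + 4 − 116) = 0 and 4, so there may be anywhere from 0 to 4 new cases. The planned counts cannot narrow this range.

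**3. Rises below the cut-off.** A rise from 385 to 445 ms is 445 − 385 = 60 ms. It crosses none of the three cut-offs and does not qualify the subject for the summary of those ever above 450 ms.

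**4. Which on-treatment ECGs are summarised.** Outside the citalopram/escitalopram subset, only Week 8 is. SAP 8.9 assigns End of Treatment, ET and unscheduled records to visit windows. Such a record can stand in for Week 8 only if it falls on days 53 to 80 and there is no scheduled Week 8 record. The windows run to Week 171 (target day 1197), so most End of Treatment ECGs would fall in windows that 9.9.5 does not tabulate. A late value above 450 ms can bring a subject into the ever-above-450 summary, but that summary shows the subject's Screening and Week 8 values.

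**5. Size: illustration on assumed inputs.** The documents give no QTcF distribution, sex split or RBBB frequency. Only N = 116 is theirs. Assumed: 40–60% women, female QTcF mean 415–425 ms, total SD 15–20 ms, within-subject SD 8–12 ms, normal distributions, no drug effect.

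Expected women entering above 450 ms = N × (proportion of women) × P(450 < X ≤ 460) / P(X ≤ 460).

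- Low end (40%, mean 415, SD 15): 46.4 × (0.0098 − 0.0013) / 0.9987 ≈ 0.4.
- High end (60%, mean 425, SD 20): 69.6 × (0.1056 − 0.0401) / 0.9599 ≈ 4.8.

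Simulation of paired Screening and Week 8 values over the same inputs gave about 0.4 to 6.0 women above 450 ms at Week 8, of whom 6% to 44% were already above at Screening. Fewer than 0.1 were above 480 ms. RBBB subjects are not included.

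**The case against.** Much can be said for the plan.

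- The same categories are shown at Screening and Week 8, so pre-existing values are visible in aggregate. The summary of subjects ever above 450 ms shows, at group level, whether their values were already high. Both points stand, but neither links a subject's two values, and the second pools new with persisting cases.
- ECG results are listed, so individual pairs can be traced. Under Protocol 7.1.1, an abnormal ECG that is clinically significant and leads to intervention or diagnosis is an adverse event, and SAP 9.9.1 counts new or worsened events. A clinically important prolongation would therefore not vanish. A listing is still not a planned summary, and a rise without clinical action would not reach the event tables.
- Protocol and SAP agree on observed ECG values only. That is a consistent choice, so the missing change analysis is a weakness of method and not a contradiction.
- A paired analysis would not establish causality. There is no control arm. The Switch Screening ECG is taken on tetrabenazine, and Schedule B takes the Rollover ECG from C-15 at Week 12 or before, possibly on blinded drug. This stands and limits the fix. In the simulation, moreover, 56% to 94% of Week 8 values above 450 ms (100 − 44 and 100 − 6) were new with no drug effect at all. A new-onset count should therefore be read with the distribution of change.

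A reader might infer that all three counts are inflated by entry values, or that Screening values are themselves counted as on-treatment findings. The entry limits rule out the first for eligible subjects, and the separate Screening summary rules out the second. A reader might also infer that QT effects cannot be assessed at all. The listings, group summaries and event tables show that this goes too far.

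**Conclusion.** The gap is real but narrow. SAP 9.9.5 has no within-subject QTcF summary, so the Week 8 count above 450 ms mixes new values with persisting ones in women who entered above 450 and up to 460 ms and in RBBB subjects who entered above 450 and up to 480 ms. Rises that stay below 450 ms are flagged nowhere in the tables. The End of Treatment/ET ECG is left out of the summaries although the protocol endpoint is on-treatment QTcF.

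The number of subjects in the mixed row cannot be derived from the documents. The illustrated 0.4 to 4.8 women entering above 450 ms rests on assumed distributions and may mean fewer than one subject. The statement that the rows above 480 and 500 ms are clean assumes that item 11 was applied and takes the eligibility ECG as the comparison. The case for change rests on the missing paired information, not on a count. It is an inexpensive improvement to the plan; no planned analysis is invalidated.

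**What to change.** In SAP 9.9.5, add for each cohort:

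- change in QTcF from the reference ECG, with the number and percentage of subjects with increases above 30 and above 60 ms;
- the number with new QTcF above 450 ms, meaning a reference value at or below 450 ms and a later value above it.

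Report both at Week 8, at End of Treatment/ET and for the maximum on-treatment value. Report QTcF above 480 and 500 ms for any on-treatment ECG, and restore the on-treatment qualifier in SAP 7.2. Because a maximum rises with the number of ECGs, show the citalopram/escitalopram subset separately.

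Name the reference ECG:

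- **Switch:** the Screening ECG, labelled as taken on tetrabenazine.
- **Rollover:** the last ECG before Day 1 of First-HD. This follows from SAP 8.7, since Schedule B has no ECG at C-15 Week 13 or the C-16 Baseline visit. Reconcile it with the Schedule B note that takes screening data from C-15 Week 12 or before, so that the Screening column and the reference value are not silently different records.

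The cost is SAP text and one extra table from ECGs already collected. The result stays descriptive, and for Switch subjects the change compares SD-809 with tetrabenazine, not with no treatment.
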